### 9.4.4. Left Ventricular Ejection Fraction

The following criteria will be used to flag left ventricular ejection fraction (LVEF) values that are values of potential clinical importance:

To identify LVEF values of potential clinical importance, NCI-CTCAE v4.0 will be used to assign categories that align with the grades for 'Ejection fraction decreased'.

LVEF Parameter	Potential Clinical Importance (PCI) Range	Unit
Absolute change from	• No change or any increase	%
baseline LVEF	Any decrease	
	$\circ$ >0-<10 decrease	
	○ 10-19 decrease	
	$\circ \geq 20$ decrease	
	○ $\geq$ 10 decrease and $\geq$ LLN	
	$\circ \geq 10$ decrease and below LLN	
	○ $\geq$ 20 decrease and $\geq$ LLN	
	$\circ \geq 20$ decrease and below LLN	
Relative change from	• $\geq 20$ decrease and $\geq LLN$	%
baseline LVEF	• ≥20 decrease and below LLN	

# 9.5. Disposition of Subjects

A summary of the number of subjects in each of the analysis populations described in Section 6 will be provided. A listing of subjects included or excluded from each of analysis populations will also be provided.

The following summaries will be provided:

- Number (%) of subjects who are still on-therapy (based on the 'Study Treatment Discontinuation' page not completed)
- Number (%) of subjects who discontinued the study treatment (based on the 'Study Treatment Discontinuation' page)
- Primary reason for study treatment discontinuation (based on the 'Study Treatment Discontinuation' page)
- Number (%) of subjects who have entered the survival follow up (based on the 'Study Treatment Discontinuation' page)
- Number (%) of subjects not being followed for study evaluation

A summary of the number and percentage of subjects who completed the study treatment as well as prematurely discontinued/withdrew from the study treatment will be displayed. Reasons for discontinuation/study treatment withdrawal will be presented by cycle, overall, and by cohort.

A listing of study completion and discontinuation/withdrawal will be generated which will include last dose date, and reasons for study treatment discontinuation/withdrawal.

#### 9.6. **Protocol Deviations**

Major protocol deviations are defined as those deviations from the protocol likely to have an impact on the perceived efficacy and/or safety of study treatments. Major protocol deviations

and any action to be taken regarding the exclusion of subjects or affected data from specific analyses are defined in protocol deviation plan.

The number and percentage of subjects in the mITT population with any protocol deviation will be tabulated by deviation category. All protocol deviations will be summarized and listed including inclusion/exclusion deviations as well as other deviations. The major protocol deviations will be flagged.

# 9.7. Demographic and Baseline Characteristics

The demographic characteristics (i.e., age, race, ethnicity, sex, baseline height, and baseline body weight, childbearing potential, Karnofsky/Lansky performance status, and body surface area (BSA)) will be summarized and listed. Age, height, weight and BSA will be summarized using the mean, standard deviation, minimum, median, and maximum. Categorical data (i.e., sex, age groups: 1 year to <2 years, 2-<12 years, 12-<18 years, race, ethnicity,

Karnofsky/Lansky performance status, woman of childbearing potential) will be summarized by frequency counts and percentages; the number and percentage of subjects with missing data will be provided.

Disease history and characteristics at initial diagnosis and screening will be summarized and listed. This summary will include the following: for solid tumor, summarize primary tumor type, location of primary tumor type, histological grade, stage at screening, time since initial diagnosis, and time since most recent relapse/progression to start of study drug, TNM staging at screening for primary tumor, regional lymph nodes and distant metastasis, metastatic disease location and time since initial diagnosis; for neuroblastoma, summarize bone marrow lesions, staging at initial diagnosis and staging at screening. The summay will also include subject tibial growth plate status and its evidence of thickening.

Medical history and ongoing conditions, including cancer-related conditions and symptoms entered on eCRF will be listed by cohort using reported term. Separate listing will be presented for liver disease medical conditions

Prior anti-cancer therapy will be coded using the World Health Organization Drug Dictionary (WHO-DD), then listed and summarized by ATC class, preferred term, overall and cohort by means of frequency counts and percentages. A summary of the number of prior anti-cancer therapy regimens will also be produced.

Prior anti-cancer radiotherapy and prior cancer related surgeries will be summarized and listed.

### 9.8. Concomitant Medications

Concomitant medications include medications (other than study drugs) starting on or after the start date of study treatment or medications starting prior to the start date of study treatment and continuing after the start date of study treatment.

Concomitant medications will be coded using the World Health Organization Drug Dictionary (WHO-DD), and summarized by lowest ATC class and preferred term using frequency counts and percentages.

These summaries will include:

- 1. Medications starting on or after the start of study drug but no later than 28 days after last dose of study drug and
- 2. Medications starting prior to start of study drug and continuing after the start of study drug.

All concomitant medications will be listed. Any concomitant medications starting and ending prior to the start of study treatment or starting more than 28 days after the last date of study treatment will be flagged in the listing.

The safety population will be used for all concomitant medications tables and listings.

# 10. Efficacy

All efficacy analyses will be based on mITT population unless otherwise specified. All analyses will be presented by cohort.

Subjects from different disease cohorts are assigned to one of the following categories for assessment of response: a) the revised RECIST guideline (version 1.1) for solid tumor and measurable disease, b) Response Criteria for neuroblastoma with I-MIBG positive lesions, (neuroblastoma subjects who do not have MIBG positive lesions should be assessed for response as solid tumor subjects with measurable disease), c) RECIST-based and/or Alpha Fetoprotein (AFP)-based response for hepatoblastoma. Investigator assessments will be considered as primary assessments. For more detailed information, see protocol Section 10.

## 10.1. Primary Efficacy Analysis

#### **Objective Response Rate (ORR)**

The primary aim of the study is to determine the investigator-assessed objective response rate of pazopanib in children, adolescents and young adults (subjects) with relapsed or refractory rhabdomyosarcoma, non-rhabdomyosarcomatous soft tissue sarcoma, and Ewing sarcoma.

Objective Response Rate (ORR) is defined as the percentage of subjects achieving either a complete or partial tumor response as per response criteria. The response rate will be calculated from the investigator review. Confirmation will be based on the disease assessment performed 1 cycle or the next scheduled visit after the initial response. The objective response rate will be computed for the 3 tumor types of primary interest.

In other words, ORR = (number of subjects with a confirmed BOR of CR + number of subjects with a confirmed BOR of PR) divided by the total number of subjects in the cohort. The assessment of activity of treatment within each histology cohort will be based on the decision rule outlined in Section 3 in this RAP.

Analyses of the primary endpoint will also be done on the mITT and Per-Protocol populations based on all cumulative data collected up to the final database lock date.

Refer to Table 1, Table 2 and Table 3 in Protocol section 10.7 for response criteria at each disease assessment and derivation of best overall response (BOR).

90% confidence intervals will be provided to characterize the variability around the response rate.

All data relating to response from the investigator will be listed including lesion measurements, response assessments and best overall response.

A waterfall plot of the best percent change in target lesions from baseline until disease progression will be provided. The plot will be pattern-coded for best overall response.

Indication of the subject number, cohort and best overall response will also be provided in the plot of duration of exposure to study treatment.

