# 3. Study Design

Pazopanib will be administered orally once daily as a tablet at a dose of 450 mg/m^2/dose or as a powder in suspension at a dose of 225 mg/m^2/dose. 450 mg/m^2/dose was the MTD for tablet as determined by Study ADVL0815, the COG Phase I study, while the dose for oral suspension of 225 mg/m^2/dose exceeds the protocol-specified MTD of 160 mg/m^2/dose established in the same study. This decision was driven by the considerations that the 160 mg/m^2/dose may result in suboptimal exposure for efficacy and that only two isolated and reversible laboratory-defined DLTs were observed at 225 mg/m^2/dose in Study ADVL0815. The maximum dose to be administered daily for tablets is 800 mg and for suspension 400 mg. Each cycle will be defined as 28 days.

The first subjects enrolled who receive powder suspension will be expected to complete extended pharmacokinetic (PK) sampling in order to obtain PK and safety data in 6 evaluable subjects. If the 225 mg/m^2/dose is not tolerated ( $\geq$ 2 subjects with dose limiting toxicities (DLTs) in the first 6 evaluable subjects), all subsequently enrolled subjects will receive 160 mg/m^2/dose and an additional 6 subjects will be assessed for safety review and PK analysis.

The primary endpoint will be objective response rate by protocol-specified, disease-specific response criteria. The best response of disease to pazopanib will be examined separately in each of the seven disease cohorts.

	Cumulative Number of Responses	Decision
Stage 1: Enter 10 subjects	0	Terminate the cohort: agent ineffective
	1 or more	Inconclusive result, continue cohort (proceed to Stage 2)
Stage 2: Enter 10 additional subjects	2 or less	Terminate the cohort: agent ineffective
	3 or more	Terminate the cohort: agent effective

The following two stage design (Simon, 1989) will be used in each cohort.

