#### 4.2. End of Stage 1 Analysis

This is a 2-stage design and therefore implies an analysis for futility based on the number of responders observed in Stage 1. The cut-off date for end of stage 1 analysis will be defined after the last subject enrolled in Stage 1 in the three cohorts of primary interest completes 20 weeks of treatment or discontinues early (as described in the previous section). Enrollment in the rhabdomyosarcoma cohort was put on temporary halt following end of enrollment in Stage 1 for all cohorts in order to assess the benefit-risk based on the overall data from Stage 1 subjects. Two subjects already pre-identified to participate in the study before assessment of benifit.risk of stage 1 were enrolled in Stage 2 at that time.

Therefore, the data-cut off date for the end of Stage 1 analysis is defined as the date when all subjects (including subjects enrolled in stage 2 for the rhabdomyosarcoma cohort) in the three cohorts of primary interest complete 20 weeks of treatment or discontuine early.

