# 4.3. Primary Analysis

The primary analysis of the study will be performed 20 weeks after the last subject's first visit in the three cohorts with tumors of primary interest, i.e. rhabdomyosarcoma, nonrhabdomyosarcomatous soft tissue sarcoma, or Ewing sarcoma/peripheral PNET. This analysis would be performed after the completion of stage 2 of the primary cohorts. However, this primary analysis will not be performed if the study is declared futile based on the statistical criteria described in Section 3 and/or clinical assessment of benefit-risk with the

end of stage 1 analysis.

Key efficacy and safety data were analysed in the end of stage 1 analysis (with a cut-off date of 31-Jan-2019) and the Request for Modification #06 of the Votrient Paediatric Investigation Plan, was submitted to the PDCO. The study was declared futile based on the clinical assessment of benefit-risk at the end of stage 1 and the decision to terminate the study was approved based on PDCO feedback.

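### Does SAP 10.1 leave a cohort that closed part-way through Stage 2 without a sound verdict on activity?

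*SAP*

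**What the plan says.** SAP 10.1 ties the reading of each cohort to the two-stage table: "The assessment of activity of treatment within each histology cohort will be based on the decision rule outlined in" SAP Section 3. With no responses in the first 10 the cohort stops as ineffective. With at least one, the table calls the result inconclusive and sends the cohort on. The last two rows (two or fewer: ineffective; three or more: effective) sit under the heading "Stage 2: Enter 10 additional subjects".

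SAP 4.2 records that "Enrollment in the rhabdomyosarcoma cohort was put on temporary halt following end of enrollment in Stage 1 for all cohorts", and that two subjects identified beforehand "were enrolled in Stage 2 at that time". SAP 4.3 then says: "The study was declared futile based on the clinical assessment of benefit-risk at the end of stage 1". It also provides that "this primary analysis will not be performed if the study is declared futile". SAP 10.1 nevertheless keeps analyses of the primary endpoint "based on all cumulative data collected up to the final database lock date".

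The only written exemption from the rule (SAP 10.2, protocol 9.8.2.2) is for non-primary cohorts with fewer than 10 patients. SAP 9.1 asks the study team, after termination, to review which analyses still make sense. SAP 8.4 says that no formal hypothesis is tested, and protocol 9.7.3 calls the 90% limits descriptive.

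**The concern.** SAP 10.1 sends every histology cohort to a rule that can end only at 10 or at 20 patients, while the SAP's own account points to a primary cohort stopped in between. The exemption in SAP 10.2 does not reach a primary cohort with more than 10 patients. The situation was also known when the plan was written: "Key efficacy and safety data were analysed in the end of stage 1 analysis (with a cut-off date of 31-Jan-2019"), and the SAP dates from September and December 2019.

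At stake is a word in the report. If the cut-off of two or fewer were read onto about 12 patients, the cohort could be called ineffective on too little data. If it were not, the label would seem to be left to choice once the responses are known. A related worry is that protocol 3.1.4 lets a cohort be closed because of results in other cohorts, so that the stated power of 0.88 might be too high.

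**Working it through.** **Inputs.** From SAP Section 3 and protocol 9.2: 10 patients in Stage 1, stop at 0 responses; 10 more in Stage 2, effective at 3 or more of 20; response rates 5% and 25%. From SAP 4.2: two Stage 2 patients in rhabdomyosarcoma. Assumption: closure at 10 + 2 = 12. The documents give neither the final number nor the responses. That the cohort passed Stage 1 is inferred from its entry into Stage 2 and the expansion condition in SAP 4.1.

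**Formula.** With X1 responses among the first 10 and n2 further patients,

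P(effective) = Σ over x = 1..10 of P(X1 = x) × P[Bin(n2, p) ≥ max(0, 3 − x)].

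**The plan's own figures (n2 = 10).**
- At p = 0.05, stopping early: 0.95^10 = 0.599. Expected size: 10 + 10 × (1 − 0.599) = 14.0.
- At p = 0.05, P(X1 = 1) = 0.3151, P(X1 = 2) = 0.0746, P(X1 ≥ 3) = 0.0115. Type I error: 0.3151 × 0.0861 + 0.0746 × 0.4013 + 0.0115 = 0.069.
- At p = 0.25, P(X1 = 0) = 0.0563, P(X1 = 1) = 0.1877, P(X1 = 2) = 0.2816, P(X1 ≥ 3) = 0.4744. Power: 0.1877 × 0.7560 + 0.2816 × 0.9437 + 0.4744 = 0.882.

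All four agree with the stated 60%, 14, 0.07 and 0.88.

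**The misreading at 12 (n2 = 2, same cut-off).**
- Power at 25%: 0.1877 × 0.0625 + 0.2816 × 0.4375 + 0.4744 = 0.609. The false-negative rate is 1 − 0.609 = 0.39, against 1 − 0.882 = 0.12 at 20, about 3.3 times as high.
- Given at least one response in the first 10: (0.3907 − 0.0563)/0.9437 = 0.354, against (0.1180 − 0.0563)/0.9437 = 0.065. This ratio, about 5.4, holds only for a cohort that has already passed Stage 1. It should not be set beside the unconditional 0.88.
- Type I error at 5% falls to 0.020.

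**What the table says of each state at 12.**

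| Responses | Reading | Reason |
|---|---|---|
| 0 of the first 10 | ineffective | the Stage 1 row is final |
| at least 1 of the first 10, total 1 or 2 of 12 | inconclusive | the Stage 2 rows require the further 10 patients |
| at least 1 of the first 10, total 3 or more of 12 | effective | the count cannot fall by 20 |

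The arithmetic supports the middle row. From 1 of 12, the chance of reaching 3 by 20 at a true 25% is P[Bin(8, 0.25) ≥ 2] = 0.63; from 2 of 12 it is 1 − 0.75^8 = 0.90. The exact 90% intervals are 0.4% to 33.9% for 1 of 12 and 3.0% to 43.8% for 2 of 12. Both contain 5% and 25%, so the interval that SAP 10.1 already requires would itself show that the data do not settle the question.

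**The case for a change.** The strongest case for a change is that the authors saw the need for a written rule when a small cohort stops, since they wrote one for non-primary groups, and left out the case that had arisen. SAP 9.1 promises a review but names no outcome, and SAP Section 1 wants analysis decisions settled before the database is frozen. A sentence would cost almost nothing.

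Part of this stands: the plan nowhere says that the Stage 2 rows apply only to cohorts that completed Stage 2. But the heading of those rows carries that meaning, and calling the cohort ineffective would mean reading them against it. A sentence written into this SAP would not be blind to the data either, because key efficacy data had been analysed at the January 2019 cut-off. It would record the natural reading without protecting it from hindsight. The study was also stopped on a clinical judgement of benefit and risk, so no stopping decision is recorded as resting on this label.

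The point about power does not stand. The figure 0.88 describes the two-stage rule and is correct for it. Closure under protocol 3.1.4 is discretionary, and the documents do not say it was used. Assuming it is always used and that three or more Stage 1 responses count as success, power at 25% would run from 0.74 (other two primary cohorts at 5%) to 0.88 (both at 25%). Those are figures for a different, assumed procedure.

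**Conclusion.** No change follows. The plan omits a clarification that a competent analyst supplies from the table itself: a cohort with at least one response in the first 10, fewer than three in all, and fewer than 20 patients remains inconclusive and is described by its response rate and 90% interval. SAP 4.3, 8.4 and 9.1 point the same way.

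The misreading would be costly if made (false-negative rate 0.39 instead of 0.12 at a true 25%), but it goes against the table's own heading. That size rests on an assumed closure at 12 and on the inference that rhabdomyosarcoma passed Stage 1. The conclusion that no change is needed depends on neither, since the same reading serves any closing size from 11 to 19. The stated 0.07 and 0.88 stand.

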# 10.2. Secondary Efficacy Analyses

#### **Objective Response Rate (ORR)**

The objective response rate will be computed for the 4 tumor types of secondary interest osteosarcoma, neuroblastoma (measurable), neuroblastoma (evaluable) and hepatoblastoma. The analysis method will be the same as that described in Section 10.1 (Primary Efficacy Analyses).

If recruitment is stopped in the non-primary histology group(s) and it has less than 10 subjects, the response data will display summary statistics and the rule in the table under Section 3 in this RAP will not apply.

The detailed response criteria for hepatoblastoma subjects are provided in Protocol section 10.6, and displayed in Table 4 in Protocol section 10.7.

#### **Progression-Free Survival (PFS)**

Progression-Free survival (PFS) is defined as the interval between the date of first dose of protocol therapy and the earliest date of disease progression or death due to any cause.

Progression will be based on the investigator assessment. Subjects are considered to have progressive disease if they have documented progression based on radiologic assessment as determined by investigator review (defined in protocol section 10). The date of death should be taken from the Death page in eCRF. Death on study due to any cause will be included. For subjects who do not progress or die, progression-free survival will be censored at the date of last adequate assessment prior to starting new anti-cancer therapy.

If there is no adequate baseline assessment, the subjects will be censored at their treatment start date. Subjects without any adequate post-baseline tumor assessments will also be censored at their treatment start date.

For subjects who receive subsequent anti-cancer therapy the following rules will apply:

- If the start date of the anti-cancer therapy is partial (i.e. either missing the day but has the month and year available or missing both day and month), the imputation rules described in Section 9.2.5.4 will be applied. No imputation will be made for completely missing dates.
- If anti-cancer therapy is started without documented disease progression or is started prior to documented disease progression, then PFS will be censored at the date of the last adequate assessment that is no later than the date of initiation of anti-cancer therapy (i.e. if an assessment occurs on the same day as the start of new anti-cancer therapy the assessment will be used as it will be assumed the assessment occurred prior to the administration of new anti-cancer therapy).
- If a subject has only a baseline visit or does not have an adequate assessment that is no later than the date of initiation of anti-cancer therapy, PFS will be censored at the treatment start date.

If a subject has neither progressed nor died nor started new anti-cancer therapy, then PFS will be censored at the date of the last adequate assessment defined as an assessment where the Investigator determined is CR, or PR, or SD. The date of assessment will be used as the censoring date.

A summary of the assignments for progression and censoring dates for PFS are specified in the following table.

Situation	Date of Event (Progression/Death) or Censoring	Outcome Event (Progression/Death) Or Censored
No (or inadequate) baseline tumor assessments	Treatment start date	Censored
No post-baseline assessments and the subject has not died (if the subject has died follow the rules for death indicted at the bottom of the table)	Treatment study date	Censored

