- ^{11.} Bone marrow evaluation to be done only in patients with known marrow involvement.
- ^{12.} Disease evaluation should be performed during Days 24 28 of the cycle for the first 2 assessments (prior to Cycles 3 and 5) and during Days 21 28 of subsequent indicated cycles. Patients who achieve a PR or CR should undergo the appropriate disease evaluation on the next consecutive cycle after initial documentation of either a PR or CR. If the institutional investigator determines that the patient has progressed based on clinical or laboratory evidence, the investigator can remove the patient from protocol therapy, he/she may opt not to confirm this finding radiographically. ; however an end of study disease assessment should be completed.
- ^{13.} For hepatoblastoma patients only perform no more than 48 hours prior to starting treatment on Day 1 of Cycle 1 (results do not need to be known) and then with each disease evaluation if the initial value is elevated.
- ¹⁴ For neuroblastoma patients only VMA = vanillylmandelic acid; HVA = homovanillic test.
- ^{15.} Females of childbearing potential require a negative serum pregnancy test prior to starting treatment. Patients of childbearing potential must use an acceptable method of birth control. Abstinence is an acceptable method of birth control.
- ^{16.} See Section 5.4.6 for dose modifications regarding Left ventricular systolic dysfunction or decrease in shortening fraction.
- ^{17.} More frequent EKG monitoring is recommended for patients receiving drugs "associated" with Torsades de pointes (See Appendix IIIB) and required for Grade 2 potassium and Grade 3 calcium (confirmed by ionized calcium), magnesium and phosphorous abnormalities. See Sections 5.4.4 and 5.4.6.2.
- ^{18.} Plain radiographs of at least one tibial growth plate should be obtained in all patients prior to the first dose of protocol therapy. In patients with open growth plates, follow-up plain radiographs of the same growth plate(s) should be obtained according to Section 7.2.1.
- ^{19.} See Section 7.3 for timing of required PK sampling, and Appendix VI for the PK worksheet. No PK samples are required beyond Cycle 11
- ^{20.} Survival follow-up will be completed every 3 months

Obtain Other Studies As Needed For Good Patient Care.

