The analysis will evaluate the mITT population on PFS using data from the investigator review. PFS is defined as the interval between the date of first dose of protocol therapy and the earliest date of disease progression or death due to any cause. Patients are considered to have progressive disease if they have documented progression based on radiologic assessment as determined by investigator review (defined in Section 10). For patients who do not progress or die, progression-free survival will be censored at the date of last adequate assessment or date of last adequate assessment prior to initiation of new anti-cancer therapy if applicable. PFS will be summarized using a Kaplan-Meier survival curve. The Kaplan-Meier estimate for the median progressionfree survival time and the first and third quartiles will be presented, along with a naive approximate 90% confidence interval if there are a sufficient number of progressions or deaths.

Overall survival is defined as the time from the first dose of the study medication until death due to any cause. The OS analysis will be performed on the mITT population and summarized using a Kaplan-Meier survival curve. The Kaplan-Meier estimate for the median OS time and the first and third quartiles will be presented, along with a naive approximate 90% confidence interval if there are a sufficient number of deaths.

Details on how event and censoring times are assigned to a patient will be provided in the RAP.

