9.8.2.5 Clinical Benefit

This is defined as the percentage of patients achieving either a complete or partial tumor response or stable disease for at least two protocol scheduled disease assessments as per RECIST criteria. 90% confidence intervals will be produced to characterize the variability around the point estimate.

Time to Progression (TTP)

The analysis will evaluate the mITT population on TTP using data from the investigator review. TTP is defined as the interval between the date of first dose of protocol therapy and the earliest date of disease progression or death due to disease under study. Patients are considered to have progressive disease if they have documented progression based on radiologic assessment as determined by investigator review (defined in Section 10). TTP will be summarized using a Kaplan-Meier survival curve. The Kaplan-Meier estimate for the median time to progression and the first and third quartiles will be presented, along with a naive approximate 90% confidence interval if there are a sufficient number of events.

Details on how event and censoring times are assigned to a patient will

be provided in the RAP.

9.8.2.6 Safety Measures:

Safety data will be presented for all patients in the safety population (mITT) regardless of cohort. If there are multiple dose levels for the powder suspension formulation group, then data for each dose level will be presented in separate columns.

Clinical Laboratory Evaluations

Hematology, coagulation parameters, clinical chemistry, lipase and amylase, thyroid function tests, and UPC data will be summarized at each scheduled assessment. Hematology, coagulation parameters and clinical chemistry will be summarized by NCI-CTCAE version 4.0 and by data outside the reference range for each scheduled assessment.

Other Safety Measures

Vital signs (blood pressure, heart rate, temperature), height and weight will be listed for each patient and change from baseline will be included for blood pressure and heart rate. A descriptive summary including change from baseline pre-dose will also be presented. Individual profiles of blood pressure will be plotted by time.

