#### Time to Progression (TTP)

Time to Progression (TTP) is defined as the interval between the date of of first dose of protocol therapy and the earliest date of disease progression or death due to disease under study. Subjects are considered to have progressive disease if they have documented progression based on radiologic assessment as determined by investigator review.

The data structure on how to assign the event and censoring to a subject is same as that defined in the Table 5 under PFS analysis. TTP will be calculated as the date of event/censoring minus the date of first protocol therapy for each subject plus one.

TTP will be summarized using a Kaplan-Meier survival curve. The Kaplan-Meier estimate for the median time to progression and the first and third quartiles will be presented, along with a naive approximate 90% confidence interval if there are a sufficient number of events.

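### PFS and TTP count only radiologic progression, so patients removed for clinical progression without a scan can be censored informatively, and no planned analysis shows how much this matters

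*SAP*

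**What the plan says.** Both documents tie progression to imaging. Protocol 9.8.2.3 on PFS: "Patients are considered to have progressive disease if they have documented progression based on radiologic assessment". SAP 10.2 repeats this for PFS ("Subjects are considered to have progressive disease if they have documented progression based on radiologic assessment as determined by investigator review") and for TTP ("Subjects are considered to have progressive disease if they have documented progression based on radiologic assessment"). Death from any cause is also a PFS event. TTP runs to the "earliest date of disease progression or death due to disease under study" (Protocol 9.8.2.5), and for TTP the SAP says that "how to assign the event and censoring to a subject is same as that defined in the Table 5" used for PFS.

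Protocol 7.1, footnote 12, covers an investigator who judges on clinical or laboratory evidence that the patient has progressed. The patient may be removed from therapy, and "he/she may opt not to confirm this finding radiographically". The same footnote adds that an end-of-study disease assessment should be done.

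SAP Table 5 has no row for clinical progression. Patients without progression or death, and those who start new anti-cancer therapy first, are censored at the last assessment of CR, PR or SD. If there is none: "Subjects without any adequate post-baseline tumor assessments will also be censored at their treatment start date". Table 5 exempts patients who have died from that last rule. The only supportive PFS analysis is a repeat on the mITT population, which SAP 10 already makes the main population.

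**The concern.** A patient who stops because the investigator believes the tumour is growing, but who has no scan to show it, is recorded as not having progressed. Kaplan-Meier estimation assumes that censored patients have the same future risk as those who stay. Here the censored patients are the ones judged to be doing worst, so the curve can be too high. The first on-study scan is due before Cycle 3, at about week 8, and anyone removed earlier without a scan may contribute no follow-up at all.

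Cohorts have 10 to 20 patients, so a few such cases can move the curve visibly. There is no control arm in which the same bias would appear. Repeating the analysis on mITT cannot reveal the problem, because it reproduces the main result.

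**Working it through.** The plan states no assumed PFS or TTP figure, so there is nothing to reproduce. The size is illustrated instead.

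**Inputs.** Scans at weeks 8 and 16 follow from the schedule (before Cycles 3 and 5, 28-day cycles). The following are assumptions: exponential progression with true median 8 weeks; a share f of progressions that are clinical only; and, at first, no rescue by an end-of-study scan or by death.

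**Formula.** Let p be the probability of progressing within an 8-week interval: p = 1 − 0.5^(8/8) = 0.5. Of those at risk at the start of an interval, a fraction p·f is censored back at the previous scan (or at treatment start) and p(1−f) have an event at the next scan. The Kaplan-Meier factor per interval is

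1 − p(1−f)/(1−p·f) = (1−p)/(1−p·f).

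If clinical progression counts as an event, the factor is 1−p = 0.5, so 16-week PFS is 0.5² = 25%.

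| f | Factor (week-8 PFS) | Week-16 PFS | Share of all patients censored at treatment start (p·f) |
|---|---|---|---|
| 10% | 0.5/0.95 = 0.526 | 27.7% | 5% |
| 20% | 0.5/0.90 = 0.556 | 30.9% | 10% |
| 40% | 0.5/0.80 = 0.625 | 39.1% | 20% |

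A simulation of 200,000 patients per scenario gives the same week-16 values to within rounding (27.8%, 30.9%, 39.1%).

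**Other medians** (simulation, f = 10%, 20%, 40%), using the adult soft tissue sarcoma medians in Protocol 2.3.3. With 1.6 months, week-8 PFS reads 48%, 51%, 58% against 45%. With 4.6 months, week-16 PFS reads 60%, 63%, 70% against 57%. The direction was upward in every scenario tried.

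**With end-of-study scans.** If a fraction r of clinical-only progressors are scanned promptly and show PD, f is replaced by f(1−r). For f = 20%:
- r = 50%: 0.5/(1 − 0.5 × 0.10) = 0.526, so week-16 PFS is 27.7%.
- r = 75%: 0.5/(1 − 0.5 × 0.05) = 0.513, so week-16 PFS is 26.3%.
- All scanned about a week later (simulation): 25.6%.

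**With deaths.** If clinical-only progressors start no new therapy and die a median of 13 weeks later (assumed), they become events, but late. Simulated week-16 PFS is then 29.5%, 34% and 43% for f = 10%, 20% and 40%.

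**Ten-patient example.** Three patients are removed clinically at week 5 without a scan; scan-based events fall at week 8 (4 patients), week 16 (2) and week 28 (1). Just after week 8, PFS is 3/10 = 30% if the three count as events and 3/7 = 43% under the SAP rule. The median is 8 weeks either way.

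**The case against.** A reader might infer that all patients removed for clinical progression are censored, often on Day 1, and that PFS is therefore overstated. The documents do not support that.

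- The footnote that waives confirmation also asks for an end-of-study assessment, using the same verb as for scheduled scans. The 7.1 table lists an end-of-therapy evaluation too. PD found there before new therapy is an event.
- Death without documented progression is an event in Table 5.
- No figure shows how often removal precedes the first scan. The phase I median of 2 cycles covers stopping for any reason and coincides with the first scan, so it fits radiologic progression equally well.
- A reader might also expect the reported median to double from 8 to 16 weeks. That occurs mainly because an assumed 8-week median coincides with the first scan date. With a true median of 4.6 months, the reported median stays at 28 weeks up to f = 30%.

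The stakes are also limited. PFS and TTP are secondary and descriptive, and SAP 8.4 tests no hypothesis. SAP 4.3 records that the study had already been declared futile after stage 1. SAP 9.5 tabulates discontinuation reasons by cohort, so a patient reader could find these cases in the listings.

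All of this stands, and it makes the concern conditional. It does not remove it. Footnote 2 of the 7.1 table asks for end-of-therapy evaluations only if possible, and footnote 12 gives the end-of-study assessment no time window. Once new therapy starts before documented progression, a later scan cannot restore the event. Death, where it counts, comes later than the progression. A discontinuation table does not show what the curve would be.

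**Conclusion.** The concern holds in conditional form. The plan censors a clinical-only progressor who has no end-of-study scan showing PD before new therapy and who is alive or has started new therapy. That censoring is informative and can raise the descriptive PFS and TTP curves.

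The size cannot be fixed from the documents. In the 8-week illustration without rescue it is about 3, 6 and 14 percentage points at week 16 for shares of 10%, 20% and 40%. With a 20% share it falls to between 1 and 3 points if half to three quarters of these patients are scanned promptly. Both the share and the scan rate are assumptions, and no claim is made about the median.

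ORR and the two-stage decision rule are unaffected, because an unknown or missing response counts as non-response (Protocol 9.8.1, SAP 9.1). This is a worthwhile, inexpensive improvement to secondary endpoints.

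**What to change.** Keep the radiologic definition for the main PFS and TTP analyses. Replace or supplement the redundant mITT repeat with a sensitivity analysis of both endpoints in which discontinuation for progressive disease without radiologic PD is an event on the discontinuation date. Give this case its own row in Table 5. Report by cohort how many patients were censored for this reason, and how many of them at treatment start.

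While editing, carry the Table 5 exception for deaths into the PFS text. Give TTP its own death rule as well, since Table 5 counts any death without PD whereas the TTP definition counts only death from the disease under study.

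The cost is one extra table per endpoint, from the primary discontinuation reason already collected (Protocol 8.2) and summarized (SAP 9.5). The change can go in the RAP Addendum that SAP 8 provides for. The downside is a less objective event in an open-label, investigator-assessed trial, which is why it belongs in a sensitivity analysis. If the count is zero, the report will show that the issue did not arise.
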